# 7.8.3 Analyses of TPS, GEP and TMB

The following analyses will be performed for TPS, GEP and TMB:

- Summary statistics of the biomarker in all randomized subjects with quantifiable biomarker.
- Summary of BOR and ORR by baseline biomarker in all randomized subjects.
- For each biomarker subgroup (further specified in the DPP) at baseline:
  - OS/PFS curves for each treatment group will be estimated using the Kaplan-Meier product limit method. Two-sided, 95% confidence intervals for median OS/PFS will be constructed based on a log-log transformed CI for the survivor function S(t)
  - Forest plot of Hazard Ratios with 95% CIs.
- For GEP only, a histogram of the distribution of GEP between arms will be provided

Additional analyses may be performed to evaluate the association between these biomarkers and the efficacy.

#### 7.9 Clinical Outcomes Assessments

The outcome research analyses will be performed using all randomized subjects at the time of final analysis of OS.

The analyses of EQ-5D-3L and FACT-HN outcomes will be restricted to all randomized subjects and the randomized subjects with PD-L1 CPS  $\geq$  20 who have an assessment at baseline and at least one post-baseline assessment.

#### 7.9.1 EQ-5D-3L

The following descriptive analyses will be conducted:

- EQ-5D-3L questionnaire completion rate, defined as the proportion of questionnaires actually received out of the expected number (i.e. number of subjects on treatment or in follow up), will be calculated and summarized for each assessment time point by treatment group.
- A by-subject listing of the level of problems in each dimension, corresponding to EQ-5D-3L health state (i.e., 5-digit vector), EQ-5D-3L utility index score, and EQ-5D-3L VAS score will be provided.
- Proportion of subjects reporting problems for the 5 EQ-5D-3L dimensions at each assessment time point will be summarized by level of problem and by treatment group. Percentages will be based on number of subjects assessed at assessment time point. Separate analyses will be performed including or excluding cases with missing data
- For the EQ-5D-3L utility index and VAS scores, separately:
  - Mean score and mean change from baseline at each assessment time point will be summarized by treatment group using descriptive statistics (N, mean with SD and 95% CI, median, first and third quartiles, minimum, maximum).
  - A line graph summarizing the mean changes from baseline will be produced.

#### 7.9.2 FACT-HN

FACT-HN data will be described by treatment group as randomized in the following ways:

- Scores and post-baseline changes in scores for the following components of the FACT-HN will be summarized at each assessment time point using descriptive statistics (ie, N, mean with SD and 95% CI, median, first and third quartiles, minimum, maximum): FACT-G, PWB, SWB, EWB, FWB, HNC, FHNSI-10, FACT-HN TOI, and FACT-HN total.
- A line graph summarizing the mean changes from baseline will be produced.
- The proportion (N) of subjects with symptomatic deterioration, defined as a clinically meaningful decline in FHNSI-10 score (worsening from baseline ≥ 3 points), will be summarized at each assessment time point.
- TTSD will be estimated using the Kaplan-Meier (KM) product limit method and will be displayed graphically. A table will be produced presenting number of events, number of subjects involved, medians, and 95% CIs for the medians. Median values of TTSD, along with two-sided 95% CI in each treatment group will be computed based on a log-log transformation method.
- The proportion (N) of subjects with symptomatic deterioration, defined as a clinically meaningful decline in FHNSI-10 score (worsening from baseline ≥ 3 points), or death, will be summarized at each assessment time point.
- Time to symptomatic deterioration or death will be estimated using the Kaplan-Meier (KM) product limit method and will be displayed graphically. A table will be produced presenting number of events, number of subjects involved, medians, and 95% CIs for the medians. Median values of time to symptomatic deterioration or death, along with two-sided 95% CI in each treatment group will be computed based on a log-log transformation method.

- Proportion (N) of subjects endorsing each response option for item GP5, "I am bothered by side effects of treatment," will be summarized by treatment group at each assessment time point. Separate analyses will be performed including or excluding cases with missing data.
- Proportion (N) of subjects with post-baseline improvement, stability, or worsening in GP5 item response will be summarized by treatment group at each assessment time point (except baseline). Separate analyses will be performed including or excluding cases with missing data.

#### 8 CONVENTIONS

The following conventions may be used for imputing partial dates for analyses requiring dates:

- For missing and partial adverse event onset dates, imputation will be performed using the Adverse Event Domain Requirements Specification
- For missing and partial adverse event resolution dates, imputation will be performed as follows (these conventions may change):
  - If only the day of the month is missing, the last day of the month will be used to replace the missing day. If the imputed date is after the death date or the last known alive date, then the latest known alive date or death date is considered as the resolution date.
  - If the day and month are missing or a date is completely missing, it will be considered as missing.
- Missing and partial non-study medication domain dates will be imputed using the derivation algorithm described in 4.1.3 of BMS Non-Study Medication Domain Requirements Specification.
- Missing and partial radiotherapy and surgery dates will be imputed using algorithm described in APPENDIX 2.
- For death dates, the following conventions will be used for imputing partial dates:
  - If only the day of the month is missing, the 1st of the month will be used to replace the missing day. The imputed date will be compared to the last known alive date and the maximum will be considered as the death date.
  - If the month or the year is missing, the death date will be imputed as the last known alive date.
  - If the date is completely missing but the reason for death is present, the death date will be imputed as the last known date alive.
- For date of progression after start of study therapy, the following conventions will be used for imputing partial dates:
  - If only the day of the month is missing, the 1st of the month will be used to replace the missing day. In case of the date of death is present and complete, the imputed progression date will be compared to the date of death. The minimum of the imputed progression date and date of death will be considered as the date of progression.
  - If the day and month are missing or a date is completely missing, it will be considered as missing.

- For date of progression to prior therapies, the following conventions will be used for imputing partial dates:
  - If only the day of the month is missing, the 1st of the month will be used to replace the missing day.
  - If the day and month are missing or a date is completely missing, it will be considered as missing.
- For other partial/missing dates, the following conventions were used:
  - If only the day of the month is missing, the 15th of the month will be used to replace the missing day.
  - If both the day and the month are missing, "July 1" will be used to replace the missing information.
  - If a date is completely missing, it will be considered as missing.

The following conversion factors will be used to convert days to months or years:

1 month = 
$$30.4375$$
 days and 1 year =  $365.25$  days.

Duration (e.g. time-to onset, time-to resolution) will be calculated as follows:

Duration = (Last date - first date 
$$+ 1$$
)

Last known alive date will be defined based on all appropriate dates collected on the CRF.

All statistical analyses will be carried out using SAS (Statistical Analysis System software, SAS Institute, North Carolina, USA) unless otherwise noted.

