3.6.2 Lost to Follow-Up

All reasonable efforts must be made to locate participants to determine and report their ongoing status. This includes follow-up with persons authorized by the participant as noted above. Lost to follow-up is defined by the inability to reach the participant after a minimum of three documented phone calls, faxes, or emails as well as lack of response by participant to one registered mail letter. All attempts should be documented in the participant's medical records. If it is determined that the participant has died, the site will use permissible local methods to obtain the date and cause of death.

If investigator's use of third-party representative to assist in the follow-up portion of the study has been included in the participant's informed consent, then the investigator may use a Sponsor-retained third-party representative to assist site staff with obtaining participant's contact information or other public vital status data necessary to complete the follow-up portion of the study. The site staff and representative will consult publicly available sources, such as public health registries and databases, in order to obtain updated contact information. If after all attempts, the subject remains lost to follow-up, then the last known alive date as determined by the investigator should be reported and documented in the participant's medical records.

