#### 4 ENDPOINTS

# 4.1 Primary Endpoints

#### 4.1.1 Overall Survival

- OS in randomized subjects with PD-L1 CPS  $\geq$  20
- OS in all randomized subjects

Overall survival (OS) is defined as the time from randomization to the date of death from any cause. For subjects that are alive, their survival time will be censored at the date of last contact date (or "last known alive date"). Overall survival will be censored at the date of randomization for subjects who were randomized but had no follow-up.

OS rate at time T is defined as the probability that a subject is alive at time T following randomization.

Survival follow-up will be conducted every 3 months after subject's off-treatment date.

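### SAP section 8 ignores a recorded year of death when the month is missing, so an OS event can be dated to a year the record rules out (minor correction)

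*SAP*

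**What the plan says.** SAP section 8 has three rules for incomplete death dates, introduced by "For death dates, the following conventions will be used for imputing partial dates".

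- **Only the day missing.** The first of the recorded month is used, and then "The imputed date will be compared to the last known alive date and the maximum will be considered as the death date".
- **Month or year missing.** "If the month or the year is missing, the death date will be imputed as the last known alive date".
- **Whole date missing.** "If the date is completely missing but the reason for death is present, the death date will be imputed as the last known date alive".

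The opening sentence of section 8 is permissive about its conventions, but the death-date item is worded as an instruction, so the rule is operative. No other section overrides it.

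The imputed date feeds the primary endpoint: "Overall survival (OS) is defined as the time from randomization to the date of death from any cause" (SAP 4.1.1). Two further statements determine how far the last known alive date can lie behind the death. The first is the contact schedule, "Survival follow-up will be conducted every 3 months after subject's off-treatment date" (SAP 4.1.1). The second is the definition, "Last known alive date will be defined based on all appropriate dates collected on the CRF" (SAP 8). Neither ties the last known alive date to the recorded year of death.

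**The concern.** The middle rule joins two different situations with an *or*. If the year is missing, the last known alive date is about all there is to use. If the year is present and only the day and month are missing, the record gives a hard lower bound of 1 January of that year. The rule does not use that bound, so a year-only death gets the same date as a death with no date at all.

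When the last known alive date falls in an earlier year, the assigned date is more than imprecise: the data contradict it. The error always shortens survival for that participant. OS in all randomized participants and in those with PD-L1 CPS ≥ 20 is the basis of the trial's conclusions. Event times enter the log-rank risk sets and the Kaplan-Meier curves directly. None of the supportive OS analyses listed in SAP 7.5.7 varies the death-date imputation, so the error would not show there.

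**Working it through.** The plan states no figure on this point, so there is none to reproduce. The check has four steps.

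**1. Rules side by side** (LKA = last known alive date)

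| What is known | Date assigned | Recorded year kept? |
|---|---|---|
| Death: month and year (SAP 8) | later of first of month and LKA | yes |
| Death: year only (SAP 8) | LKA | no |
| Death: nothing (SAP 8) | LKA | not applicable |
| Procedure, or on-treatment/subsequent surgery: year only (SAP Appendix 2) | later of 1 January of the year and first dose | yes |
| Other dates: year only (SAP 8) | 1 July of the year | yes |

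SAP 8 sets some year-only dates, such as on-study progression, to missing. That loses information but does not assign a date that conflicts with the record.

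**2. Worked dates.** Death recorded as 2019, month and day unknown.

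- LKA 20-Nov-2018: the SAP rule gives 20-Nov-2018. The earliest date the record allows is 01-Jan-2019, which is 10 + 31 + 1 = 42 days later.
- LKA 03-Oct-2018: the shortfall is 28 + 30 + 31 + 1 = 90 days.
- LKA in 2019: a rule bounded by the recorded year also gives LKA, so nothing changes.

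**3. How often, and by how much.** Assumptions: the death day D is uniform over a year of 365.25 days, and the gap G between LKA and death is uniform from 0 to g days. The year boundary is crossed when G > D.

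- Share crossing: E[G] / 365.25 = g / (2 × 365.25)
- Mean shortfall to 1 January among those crossing: [g² / (6 × 365.25)] ÷ [g / (2 × 365.25)] = g / 3
- Largest shortfall: g

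| Assumed maximum gap g | Share crossing | Mean shortfall | Largest |
|---|---|---|---|
| 30 days | 4.1% | 10 days | 30 days |
| 91 days (3-monthly contact) | 12.5% | 30.3 days | 91 days |
| 98 days (with the 7-day visit window, Protocol Table 5.1-3) | 13.4% | 32.7 days | 98 days |

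A simulation of 2,000,000 records per row agrees: 4.1%, 12.4% and 13.4% crossing, with means of 10.0, 30.3 and 32.7 days.

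Averaged over all year-only deaths at g = 91, the SAP rule is early by g/2 = 45.5 days. The part that contradicts the record is 0.125 × 30.3 = 3.8 days of that.

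**4. Effect on the comparison.** The number of year-only deaths is not given. Suppose 1% of the 741 planned deaths, which is about 7. Then 7 × 0.125 = 0.9, or about one affected record.

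A simulated trial gives the scale: 930 participants, 26 months' accrual, cutoff at 51 months, control median 10.8 months, and a constant hazard ratio of 0.74. The constant ratio simplifies the plan's delayed effect.

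- Seven deaths in one arm moved 3 months earlier: hazard ratio shifts by about 0.002.
- Seven deaths in one arm moved 10.5 months earlier: about 0.008.
- The same moves spread over both arms: average shift about 0.000 to 0.001.

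**The case against.** The strongest reply is that this does not matter to the result. Survival contact is every 3 months, and Protocol 3.6 lets the sponsor request survival data outside that window. Protocol 5.4.1 counts every contact date towards the last known alive date. Year-only deaths should therefore be few and their gaps short. The present convention is simple, pre-specified and blind to arm. The 1 January bound is also still an early date: at a 91-day gap it removes only 3.8 of the 45.5 days of average error. All of this stands as to size.

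It does not justify the rule. An early-dating convention is defensible where the record is silent. Here the record speaks and is set aside, and the bounded date is already the earliest one possible.

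Three stronger readings are tempting, and the documents do not support them.

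- **Year-only deaths cluster among participants lost to follow-up.** Protocol 3.6.2 says "The site staff and representative will consult publicly available sources, such as public health registries and databases", but the stated purpose of that sentence is to update contact information. The same section tells sites to obtain the date and cause of death. Nothing says such sources return only a year.
- **Gaps run up to a year, so about half of these records cross a year boundary.** That does not fit 3-monthly contact. A last contact on 15-Feb-2019 with death recorded as 2020 would be dated at least 320 days early. This is possible for someone hard to trace, but it is not typical.
- **The error is unequal between arms because the trial is open-label.** The documents give no information on loss to follow-up by arm.

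**Conclusion.** The point holds as a minor correction. As written, SAP 8 can assign a primary-endpoint event to a year that the participant's own record excludes, while comparable rules in the same SAP respect the recorded information.

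With contact gaps of up to about 91 days, roughly one year-only death in eight would be affected, by about a month on average. Those figures rest on the uniform assumptions in the working and would rise with longer gaps. The contradiction itself depends only on the last known alive date preceding the recorded year.

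The number of events is unchanged. The effect on the hazard ratio is likely negligible, but it cannot be calculated from the documents because the count of year-only deaths is not given. The point gives no ground for doubting the trial's conclusions.

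**What to change.** In SAP section 8, replace the rule for a missing month or year, and the rule for a completely missing date, with:

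> If the year is known and the month is missing, the death date is the later of 01-Jan of the recorded year and the last known alive date. If the year is missing or the date is completely missing, the last known alive date is used.

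Keep the present condition that a completely missing date is imputed only when a reason for death is recorded.

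The change leaves untouched every record whose last known alive date already lies in the recorded year. In the remaining year-only records it moves the date to the earliest one the record allows, which is always closer to the truth. It costs one SAP sentence and one line of derivation code, and is best made before database lock.

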#### 9 CONTENT OF REPORTS

All analyses describe in this SAP will be included in the final Clinical Study Report. Refer to the Data Presentation Plan for mock-ups of all tables and listings.

#### 10 DOCUMENT HISTORY

Table 10-1: Document Revision History

Version Number	Author(s)	Description
1.0		Initial release dated 21-Oct-2019
2.0		• Per US FDA feedback, removed the second formal interim analysis (at 90% information fraction).
		• Added to Section 7.9.2 the analysis of time to symptomatic deterioration or death.
		• Corrected a typo in Table 7.4.1-3 replacing number 75 with 100.

# APPENDIX 1 TIME-TO ONSET AND TIME-TO RESOLUTION DEFINITION AND CONVENTIONS FOR SELECT ADVERSE EVENTS, IMMUNE-MEDIATED ADVERSE EVENTS AND EVENTS OF SPECIAL INTEREST

#### Time-to onset definition

Time-to onset of AE (any grade) for a specific category is defined as the time between the day of the first dose of study treatment and the onset date of the earliest AE (of any grade) in this category.

The time-to onset of AE (grade 3-5) for a specific category is defined similarly with an onset date corresponding to a grade 3-5 AE.

Time-to onset of drug-related AE (any grade or grade 3-5) for a specific category is defined similarly but restricted to drug-related AE.

Time-to onset for a specific subcategory is defined similarly but restricted to event of this subcategory.

#### Time-to resolution definition

In order to derive the time-to resolution, overlapping or contiguous AEs within a specific category or subcategory will be collapsed into what will be termed "clustered" AEs. For example, if a subject (without pre-treatment AE) experienced an AE from 1st to 5th January, another AE (with different PT but within same category) from 6th to 11th January and same AE from 10th to 12th January, these will be collapsed into one clustered AE from 1st to 12th January. Table A1-1 is summarizing key derivation steps for each type of clustered AEs.

Time-to resolution of AE (any grade) for a specific category is defined as the longest time from onset to complete resolution or improvement to the grade at baseline among all clustered AEs experienced by the subject in this category per adverse event criteria category. Events which worsened into grade 5 events (death) or have a resolution date equal to the date of death are considered unresolved. If a clustered AE is considered as unresolved, the resolution date will be censored to the last known alive date. Improvement to the grade at baseline implies that all different events in the clustered adverse event should at least have improved to the corresponding (i.e. with same preferred term) baseline grade. This measure is defined only for subjects who experienced at least one AE in the specific category.

The time-to resolution of AE (grade 3-5) for a specific category is defined similarly with an onset date corresponding to a grade 3-5 AE.

Time-to resolution of drug-related AE (any grade or grade 3-5) for a specific category is defined similarly but restricted to drug-related AE.

The time-to resolution of AE (any grade or grade 3-5, drug-related or all) where immune modulating medication was initiated is defined similarly. For data presentation not restricted to IMAE, the additional condition that the subject started an immune modulating medication during the longest AE resolution period will be applied.

Time-to resolution for a specific subcategory is defined similarly but restricted to event of this subcategory.

**Table A1-1:** Derivation of Clustered AE

Derivation
Collapse any on-treatment AE from the same category
Collapse any on-treatment drug-related
AE from the same category
Collapse any on-treatment AE from the same category.
Resolution will be based on the onset date of the earliest grade 3-5 records (if no grade 3-5 record, clustered AE is excluded)
Collapse any on-treatment drug-related AE from the same category
Resolution will be based on the onset date of the earliest grade 3-5 record (if no Grade 3-5 record, clustered AE is excluded)

The algorithm for collapsing adverse event records is using the following conventions:

For each subject and specified category, the corresponding adverse event records will be collapsed when:

- 1) Multiple adverse event records have the same onset date.
- 2) The onset date of an event record is either the same day or 1 day later than the resolution date of a preceding event record (contiguous events).
- 3) The onset date of an event record is after the onset date and prior to or on the resolution date of a preceding event record (overlapping events).

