#### 7.6.6.1 Incidence of Select AE

Select AEs will be summarized by treatment group for each category/subcategory.

The following analyses will be conducted using the 30-day safety window only:

- Overall summaries of any select AEs by worst CTC grade (any grade, grade 3-4, grade 5) presented by Category or Subcategory/PT.
- Overall summaries of any drug-related select AEs by worst CTC grade (any grade, grade 3-4, grade 5) presented by Category or Subcategory/PT.

- Overall summaries of any serious select AEs by worst CTC grade (any grade, grade 3-4, grade 5) presented by Category or Subcategory /PT.
- Overall summaries of drug-related serious select AEs by worst CTC grade (any grade, grade 3-4, grade 5) presented by Category or Subcategory /PT.
- Overall summaries of any select AEs leading to discontinuation by worst CTC grade (any grade, grade 3-4, grade 5) presented by Category or Subcategory /PT.
- Overall summaries of drug-related select AEs leading to discontinuation by worst CTC grade (any grade, grade 3-4, grade 5) presented by Category or Subcategory /PT.
- Summary of frequency of unique select AEs by Category.

A by-subject select AE listing will be provided.

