#### 7.6.6.3 Time-to Resolution of Select AE

Time-to resolution of the following specific events will be summarized separately for each category/subcategory.

- Time-to resolution of drug-related select AE (any grade, grade 3-5) by treatment group
- Time-to resolution of drug-related select AE (any grade, grade 3-5) where immune modulating medication was initiated, by treatment group

Time-to resolution analyses are restricted to treated subjects who experienced the specific events. Time-to resolution where immune modulating medication was initiated analyses are restricted to treated subjects who experienced the specific events and who received immune modulating medication during the longest select AE.

The analyses will be conducted using the 30-day safety window.

The following summary statistics will be reported: percentage of subjects with resolution of the longest select AE, median time-to resolution along with 95% CI (derived from Kaplan-Meier estimation) and ranges.

See time-to resolution definition subsection of APPENDIX 1 for additional details.

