# 7.6.7 Immune-Mediated Adverse Events (US Submission)

IMAEs will be summarized by treatment group for each immune-mediated category / PT using the 100-day safety window:

- Overall summary of non-endocrine IMAEs by worst CTC grade (any grade, grade 3-4, grade 5) where immune modulating medication was initiated presented by Category / PT.
- Overall summary of endocrine IMAEs by worst CTC grade (any grade, grade 3-4, grade 5) presented by Category / PT.
- Overall summary of non-endocrine IMAEs leading to discontinuation by worst CTC grade (any grade, grade 3-4, grade 5) where immune modulating medication was initiated presented by Category / PT.
- Overall summary of endocrine IMAEs leading to discontinuation by worst CTC grade (any grade, grade 3-4, grade 5) presented by Category / PT.
- Overall summary of non-endocrine IMAEs leading to dose delay or reduction by worst CTC grade (any grade, grade 3-4, grade 5) where immune modulating medication was initiated presented by Category / PT
- Overall summary of endocrine IMAEs leading to dose delay or reduction by worst CTC grade (any grade, grade 3-4, grade 5) presented by Category / PT.
- Summaries of time-to onset and time-to resolution of non-endocrine IMAEs where immune modulating medication was initiated presented by Category.
- Summaries of time-to onset and time-to resolution of endocrine IMAEs presented by Category.

A by-subject listing of IMAEs will be provided. By-subject listings of time-to resolution for longest IMAEs cluster (any grade and grade 3-5 in separate summaries) will also be provided. For new studies which collect investigator assessment of potential IMAE data, a by-subject listing of AEs considered as immune-mediated events per investigator but not qualified for IMAEs definition will also be provided.

In addition, for all nivolumab treated subjects who experienced at least one IMAE, the following data presentation will be provided:

- Summary of subjects who were re-challenged with nivolumab by IMAE category, with extended follow-up
- Summary of subjects who were re-challenged with nivolumab or ipilimumab by IMAE category, with extended follow-up

For these, re-challenge is considered to have occurred when last nivolumab and/or ipilimumab infusion was administered after the onset of an IMAE.

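### The longest-cluster rule for time to resolution compares complete durations with censored ones, so a briefly observed unresolved or fatal cluster can be passed over and the participant counted as resolved

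*SAP*

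**What the plan says.** Appendix 1 of the SAP (Time-to resolution definition) first merges the adverse event records of one category into clusters. Records merge if they share an onset date, if one starts on the day another resolves or the day after, or if they overlap: "The onset date of an event record is after the onset date and prior to or on the resolution date of a preceding event record". Episodes separated by a longer gap stay as separate clusters.

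The participant's value is then "defined as the longest time from onset to complete resolution or improvement to the grade at baseline among all clustered AEs". Two further sentences deal with events that do not resolve: "Events which worsened into grade 5 events (death) or have a resolution date equal to the date of death are considered unresolved", and "If a clustered AE is considered as unresolved, the resolution date will be censored to the last known alive date". These set the status and the length of such a cluster. Neither says that it takes precedence over a longer cluster that did resolve, and no other part of the SAP says so.

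Section 7.6.6.3 reports "percentage of subjects with resolution of the longest select AE" together with a Kaplan-Meier median, for any grade and for grade 3-5. Section 7.6.7 summarises time to resolution of immune-mediated events and adds "By-subject listings of time-to resolution for longest IMAEs cluster". In the grade 3-5 derivation, Table A1-1 drops any cluster with no grade 3-5 record.

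**The concern.** The rule takes a maximum over two kinds of number. A resolved cluster has a complete duration. An unresolved cluster has only a lower bound, cut off at the last known alive date. Comparing them as equals means that the selected cluster need not be the participant's longest event, and an event cut short by death is the one most likely to lose. The SAP deliberately classes fatal clusters as unresolved, but a rapidly fatal cluster can be dropped before that status counts.

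A second cluster in a category is foreseeable. Categories pool several preferred terms, protocol 4.5.4 lets dosing resume after a drug-related event settles, and SAP 7.6.7 plans summaries of participants re-challenged after an immune-mediated event.

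At stake are the planned aggregate statements of how often these toxicities resolve. Incidence and death tables do not answer that question.

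**Working it through.** **1. The SAP's own example.** Records run 1-5, 6-11 and 10-12 January. The second starts one day after the first ends, so they are contiguous. The third starts before the second ends, so they overlap. The result is one cluster from 1 to 12 January, as the SAP states. With the duration formula of SAP section 8 (last date minus first date, plus 1), its length is 12 - 1 + 1 = 12 days.

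**2. The same rules with two clusters.** The dates are illustrative. Cluster 1 runs from 1 January to 29 February 2020 and resolves: 31 + 29 = 60 days. Cluster 2 starts on 1 June and does not resolve.

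| Last known alive date | Length of cluster 2 | Value under Appendix 1 |
|---|---|---|
| 10 June (fatal) | 10 days | 60 days, resolved |
| 30 June (ongoing) | 30 days | 60 days, resolved |
| 29 August (ongoing) | 30 + 31 + 29 = 90 days | 90 days, censored |

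The unresolved cluster is passed over exactly when its observed length is below that of the resolved one. The resolved cluster must be the earlier one, because an open cluster absorbs later records.

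**3. Chance of being passed over, given two such clusters.** Assume that the earlier cluster has an exponential duration with mean m days and that the unresolved one is observed for c days. The chance is exp(-c/m).

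| m | c = 7 | c = 14 | c = 30 |
|---|---|---|---|
| 60 days | 89% | 79% | 61% |
| 30 days | 79% | 63% | 37% |

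**4. Effect on the reported percentage.** Let q be the share of participants in the table with two separate clusters, u the share whose last cluster is unresolved, and p the chance that it is passed over. The overstatement is q × u × p. The documents give none of these, so the ranges are assumptions.

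- Both lengths from the same exponential distribution, so p = 1/2:
  - q = 10%, u = 20%: 0.10 × 0.20 × 0.5 = 1.0 point. Simulation gave 81.0% resolved against 80.0%.
  - q = 40%, u = 50%: 0.40 × 0.50 × 0.5 = 10 points. Simulation gave 59.9% against 49.8%.
- Short observation of the unresolved cluster. The earlier cluster has a median of 42 days, so m = 42/ln 2 = 60.6, and c is uniform on 3 to 45 days. Then p = (60.6/42) × (exp(-3/60.6) - exp(-45/60.6)) = 1.443 × (0.952 - 0.476) = 0.69:
  - q = 10%, u = 20%: 0.10 × 0.20 × 0.69 = 1.4 points.
  - q = 20%, u = 50%: 0.20 × 0.50 × 0.69 = 6.9 points.
  - q = 40%, u = 50%: 0.40 × 0.50 × 0.69 = 13.8 points.

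The sign is fixed. Every participant with all clusters resolved also has a resolved longest cluster, but not the reverse.

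**5. Effect on the median.** I simulated the short-observation inputs and compared the SAP rule with one that uses the unresolved cluster whenever there is one. The SAP rule gives a lower Kaplan-Meier median by 0.1 to 1.1 days for q of 10-20%, and by 2.8 days at q = 40%, u = 50% (65.6 against 68.4). With equal-length inputs and the same mean of 60.6 days, the gap is 0.1 to 3.6 days for q of 10-20%, and 6.6 days at the same extreme (86.8 against 93.4).

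**The case against.** The case on the other side has real force.

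- **The label is honest.** Section 7.6.6.3 says that the percentage refers to the longest event. It does not claim that the participant is free of unresolved toxicity. That stands, but the label does not tell a reader that longest was decided by setting a censored length against a complete one.
- **The grade 3-5 analysis removes part of the problem.** A long grade 1-2 cluster is excluded there and cannot displace a fatal one. Masking in that analysis needs two separate grade 3-5 clusters in one category. This stands and limits the reach.
- **Ongoing events in survivors are usually long.** The interim analysis waits until all participants have at least 12 months of follow-up, and unresolved clusters run to the last known alive date. A persistent toxicity will therefore usually be the longest cluster and be counted as unresolved. This confines the problem mainly to events that start shortly before death or cut-off.
- **Any unresolved cluster is a different quantity.** A trivial ongoing grade 1 event would override a long, severe, resolved one. This is a good reason to add the new percentage beside the existing summary rather than replace it.

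A reader might infer that fatal toxicity disappears from the safety report. It does not. Section 7.6.6.1 plans "Overall summaries of any select AEs by worst CTC grade (any grade, grade 3-4, grade 5) presented by Category or Subcategory/PT", section 7.6.7 has a grade 5 column for immune-mediated events, section 7.6.1 tabulates deaths with reasons, and by-subject listings show each event.

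A reader might also infer that the distortion falls mainly on the nivolumab plus ipilimumab arm. The documents do not support that. Protocol Table 4.5.3.2-1 provides for up to four occurrences of severe acneiform rash on cetuximab, and protocol 4.5.5.1 lists grade 3 drug-related colitis and pneumonitis of any duration as grounds for stopping nivolumab, which would limit repeat severe episodes in Arm A.

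**Conclusion.** The point holds in a limited form. As Appendix 1 is written, a participant whose unresolved or fatal cluster was observed for less time than an earlier resolved cluster in the same category counts as resolved in the time-to-resolution summaries. The error runs one way, towards a higher resolved percentage.

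Its size cannot be computed from the documents. With 10-40% of participants in a table having two separate clusters and 20-50% of last clusters unresolved, the overstatement is roughly 1 to 10 points, and about 14 if unresolved clusters are also observed only briefly. The median moves little except at the extreme of these inputs. The 37-89% figures should not be read as the share of participants misreported: they apply only to those who already have both kinds of cluster, and they rest on assumed durations.

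These are descriptive safety summaries. No primary or alpha-controlled analysis is touched.

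**What to change.** - **SAP 7.6.6.3 and 7.6.7:** beside the longest-cluster summary, report by category the number and percentage of participants with all clusters resolved, and the number with any unresolved or fatal cluster.
- **SAP Appendix 1:** state that, for this percentage, a participant with any unresolved cluster in the category is classed as unresolved.
- **Existing duration summary:** it may stay as it is, labelled as referring to the longest observed cluster.

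No new data are needed, since cluster dates and status are already derived. The cost is one more table row and a slightly less favourable resolution percentage, because a low-grade ongoing event also counts as unresolved. Showing the two percentages side by side lets a reader see how much of the difference comes from such participants.
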